#### A non CABG related minor bleeding event will be defined using TIMI criteria as:

• any clinically overt sign of haemorrhage that was associated with a fall in haemoglobin concentration of 3 to <5 g/dL

## A CABG related major bleeding event will be defined using TIMI criteria as any of the following bleeding events that were CABG related:

- Fatal bleeding (bleeding that directly results in death
- Perioperative intracranial bleeding
- Reoperation following closure of the sternotomy incision to control bleeding
- Transfusion of greater than or equal to 5 units of whole blood or PRBCs within a 48 hour period
- chest tube output > 2 L within a 24 hour period

*t* The three organ sites included in the primary objective are gastrointestinal and urogenital, in addition to intracranial.

## Table 2.Haemorrhage outcomes (Bleeding Academic Research Consortium
[BARC] definitions for use in the secondary and exploratory
objectives only)

#### Type 0

• No bleeding

Type 1

 Bleeding that is not actionable and does not cause the patient to seek unscheduled performance of studies, hospitalization, or treatment by a healthcare professional; may include episodes leading to self-discontinuation of medical therapy by the patient without consulting a healthcare professional

Type 2

Any overt, actionable sign of haemorrhage (eg, more bleeding than would be expected for a clinical circumstance, including bleeding found by imaging alone) that does not fit the criteria for type 3, 4, or 5 but does meet at least one of the following criteria: (1) requiring nonsurgical, medical intervention by a healthcare professional, (2) leading to hospitalization or increased level of care, or (3) prompting evaluation

## Table 2.Haemorrhage outcomes (Bleeding Academic Research Consortium
[BARC] definitions for use in the secondary and exploratory
objectives only) (continued)

#### Type 3

Type 3a

- Overt bleeding plus hemoglobin drop of 3 to <5 g/dL\* (provided haemoglobin drop is related to bleed)
- Any transfusion with overt bleeding

Type 3b

- Overt bleeding plus hemoglobin drop ≥5 g/dL\* (provided haemoglobin drop is related to bleed)
- Cardiac tamponade
- Bleeding requiring surgical intervention for control (excluding dental/nasal/skin/haemorrhoid)
- Bleeding requiring intravenous vasoactive agents

Type 3c

- Intracranial haemorrhage (does not include microbleeds or haemorrhagic transformation, does include intraspinal)
- Subcategories confirmed by autopsy or imaging or lumbar puncture
- Intraocular bleed compromising vision

Type 4: CABG-related bleeding

- Perioperative intracranial bleeding within 48 h
- Reoperation after closure of sternotomy for the purpose of controlling bleeding
- Transfusion of ≥5 U whole blood or packed red blood cells within a 48-h period+
- Chest tube output  $\geq$  2L within a 24-h period

Type 5: fatal bleeding

Туре 5а

 Probable fatal bleeding; no autopsy or imaging confirmation but clinically suspicious

Type 5b

• Definite fatal bleeding; overt bleeding or autopsy or imaging confirmation

CABG indicates coronary artery bypass graft. Platelet transfusions should be recorded and reported but are not included in these definitions until further information is obtained about the relationship to outcomes. If a CABG-related bleed is not adjudicated as at least a type 3 severity event, it will be classified as not a bleeding event. If a bleeding event occurs with a clear temporal relationship to CABG (ie, within a 48-h time frame) but does not meet type 4 severity criteria, it will be classified as not a bleeding event. \*Corrected for transfusion (1 U packed red blood cells or 1 U whole blood=1

g/dL hemoglobin).

*†Cell saver products are not counted.* 

#### 9 Research Methods

#### 9.1 Study Design

This study will be a observational, population-based cohort study with a contextual comparator (reference cohort) utilising the technique of cohort event monitoring (with retrospective patient chart review) to study the short-term (up to 12 weeks) safety and use of rivaroxaban in combination with standard oral antiplatelet therapy in patients following an ACS event, as initiated by specialist HCPs in the secondary care hospital setting. Secondary use of medical records information will be used in this study as specialist HCPs will be asked to abstract information from patient medical charts onto a questionnaire.

Twelve weeks observation is regarded as a period of time sufficient for data from all relevant patient populations (which informs on any post initiation health events related to short-term exposure that they might have experienced) to be recorded in medical charts.

In addition to the desire to study the use of rivaroxaban in combination with standard oral antiplatelet therapy in a population that is more heterogeneous than those observed in clinical trials, it is also desirable to put these observations into context. This will be achieved through comparison with current standard care treatments for the prevention of atherothrombotic events following an ACS in order to examine treatment decisions and differences. Therefore, a contextual cohort of evaluable patients treated with current standard treatment of care (dependent on clinical manifestation, early management and subsequent surgical intervention) will be recruited concurrently in order to characterise the adoption of rivaroxaban into clinical practice and the prevalence of (non-clinical) reasons for prescribing and those clinical characteristics which are known risk factors for the primary outcomes of interest.(14) To avoid confusion, for the contextual cohort, patients who receive other factor Xa inhibitors or direct thrombin inhibitors will be excluded from the study.

According to the forthcoming NICE appraisal scope document for the use of rivaroxaban in the treatment of  $ACS^2$  (15) the following possible contextual comparators have been

<sup>1 Non-clinical reasons for prescribing include: factors associated with accumulation of authoritative evidence (formulary committee approval; recommendation from NICE; expert committee guidelines); and behavioural factors (personal expertise in treating condition; history of clinical success with similar treatments).

<sup>2 http://www.nice.org.uk/media/6F2/BD/AcuteCoronarySyndromeRivaroxabanDraftScope.pdf

identified based on different clinical needs of subgroups (the contextual comparator will be a single group consisting of all possible standard of care combinations combined) :

- Clopidogrel in combination with aspirin
- Ticagrelor in combination with aspirin
- Prasugrel in combination with aspirin
- Additional dual antiplatelet therapies (not specified above)

After the pharmacotherapeutic treatment decision has been made by the clinician, such that the most appropriate treatment based on clinical need is prescribed, a patient will be invited to participate in the study and consent obtained for access to information from secondary care medical charts and general practice primary care medical charts via the GP. Participants will be invited to take part in the study by a member of the research or clinical team. This will usually be a research nurse, or practitioner, or clinical researcher or treating clinician (junior doctor or consultant).

To allow inclusion of patients with a previous history of ACS or other co-morbidities requiring antiplatelet treatment, a modified version of the new user design will be used in this study. The new user design will be used for the anticoagulant treatment and is defined as no use of oral anticoagulants including rivaroxaban within the 6 months prior to index date in both cohorts. In the rivaroxaban cohort, naïve users are defined as those who never used any oral anticoagulants in the past and they will be distinguished from non-naïve users in the analysis. The new user design will not be applied to antiplatelet treatments; ongoing antiplatelet treatment will be allowed in both cohorts and presented by naivety status.

Study start is defined as the date that the first patient is recruited into the study (18th September 2015), and continue for a maximum of 36 months, or until the target sample size (1193 tbc) for both cohorts has been achieved (whichever is the soonest). The final cohort sizes, period of observation and the duration of the SCEM study will be dependent on the level of prescribing of rivaroxaban in combination with standard oral antiplatelet therapy by specialist HCPs in England and Wales. Data collected during later calendar time periods can be compared with earlier periods to identify any trends that may emerge. Slow uptake may impact on the ability to meet the study objectives; in this instance, further discussions with the regulatory authorities regarding study feasibility will be needed.

Patients will be observed from the date antiplatelet therapy was prescribed as part of the acute management of the ACS in both the rivaroxaban group and the contextual Version 7 Date: 30/08/2017

cohort for 13 weeks in order to allow for detection of outcomes associated with treatment initiation (this will allow for a delay between antiplatelet therapy administration as part of the acute treatment for the ACS, and the subsequent start of rivaroxaban to ensure 12 complete weeks of observation time for analysis). The index date for analysis for both groups will be defined dependent on the prescribing patterns observed in real life use. Since patient care is likely to be shared between secondary and primary care for most patients during the observation period, the patient's GP will be contacted at least 13 weeks after antiplatelet therapy start date to complete an abridged questionnaire to collect any information on outcomes of interest that they are aware of during the observation period to minimise under-reporting on selected outcomes. For the main statistical analysis, events will be censored at 12 weeks post index date, should they be reported after this time period. However, events of interest will be included and detailed in study reports even if they occurred after the 12 week time period. Where additional outcomes are identified that have not be reported by the initiating prescriber, these will be followed-up with the GP to ascertain further information.

#### 9.1.1 Strengths

- The observational and inclusive design allows for the surveillance of a diverse patient population under the care of specialist HCPs, particularly those with different characteristics in terms of underlying disease, co-morbidities and concomitant medications that would not have been included in clinical trials. Thus bias introduced through selection based on disease severity or type will be minimised. The approach also allows for surveillance of rivaroxaban when used off-label within the context of ACS.
- The prescribing of relevant pharmacological therapy should not be affected because of participation in this study, as the decision to prescribe has already been made prior to patient inclusion therefore the observational noninterventional nature of the study design is maintained.
- Data is collected on large numbers of cohorts given the relevant treatment combinations under study in conditions of routine clinical practice.
- Special populations can be characterised.

<sup>1 Overlap of data collection between SCEM and M-PEM should minimise any under-reporting of events of interest associated with the primary objective. However due consideration should be given to a) possible non-response of GPs for the long-term M-PEM study that might arise from the GP's knowledge that the patient is participating in the SCEM and b) that some patients are managed by specialist GPs purely on an outpatient basis and thus may never be officially admitted to hospital. The emphasis must be made that the two studies are complementary and participation in both is highly desirable.

- Time-dependent effects can be examined. This method is longitudinal and thus will enable more reliable examination of exposures in relation to outcomes over time.
- By obtaining patient consent, additional information from medical charts from other clinical specialities may be examined for selected outcomes.
- Extension to monitor long-term safety is possible.
- $_{\odot}$  The DSRU uses established networks of specialists in the UK to conduct such studies.

#### 9.2 Setting

#### 9.2.1 Selection of specialists

Specialists and members of their clinical team from within the secondary care hospital setting will be systematically identified across the country, facilitated where possible by existing clinical research networks, and will be invited to participate in the study prior to study start (exact date to be determined). These specialist HCPs will be informed that they will be participating in a cohort study which will monitor the use of rivaroxaban in any combination with standard oral antiplatelet therapy, in accordance with requirements within the Risk Management Plan. In addition they will be informed that a contextual cohort of patients taking standard antiplatelet combination therapy for secondary prevention following ACS will also be monitored.

#### 9.2.2 Selection of patients

The accessible study population will be that portion of the target population of interest to whom participating HCPs have access. The identification of the study population, will be through (non-probability) systematic sampling whereby all consecutively identified eligible new rivaroxaban user patients (within the context of ACS) treated by any specialist HCP (after the pharmacotherapeutic treatment decision has been made) and who provide consent (see section 10.3) will be enrolled until the desired sample size is reached. A corresponding procedure will be used for the contextual cohort. This method will be used because a probability sampling framework is not feasible and because participation within the study is not required as a condition of receiving treatment. This approach is intended to reduce conscious or unconscious selection bias on the part of the prescriber as to whom to enrol in the study, especially with regard to prognostic factors that may be related to prognosis.

New users of rivaroxaban will be comprised of rivaroxaban patients, who may or may not be naïve to anticoagulant treatment, with no use of oral anticoagulants including rivaroxaban prior to 6 months of index date and who are newly initiated by specialist HCPs after the ACS event. In the UK, when stabilised many patients may then have medicines management transferred to the GP in primary care. Thus, the GP may take on the primary role of monitoring treatment, providing prescriptions and altering the dose when necessary, with the option of referral to secondary care if and when required. Alternatively, the patient may be primarily managed within the secondary care hospital setting alone.

<sup>1 As relevant to the date that the specialist HCP registers to participate in the study Version 7 Date: 30/08/2017

By enrolling new rivaroxaban users (an inception or incidence cohort), this study avoids the introduction of a number of biases associated with existing users (including incidence/prevalence bias, survivorship bias, and follow-up bias). Furthermore, data will be available for the contextual comparator group which will have been collected prospectively during the same calendar period, for similar indications using the same data collection methods, and all subject to the same protocol.

A cross sectional random sample of investigative sites will be surveyed to explore the representativeness of the study population. Using medicines management audit information the demographic characteristics of patients treated for ACS will be examined and compared to those enrolled within this study.

Cohort recruitment will be examined regularly to monitor the number of evaluable patients included, so as to ensure that the desired ratio of 1:1 for the two exposure groups is achieved in the final overall study cohort for analysis.

#### 9.2.3 Patient Inclusion Criteria

Since this is an observational cohort study conducted in a naturalistic setting, open patient entry criteria apply to maximise external validity. The inclusion criteria are:

- Age 18 years or above
- Patients newly prescribed rivaroxaban in any combination with standard oral antiplatelet therapy for the indication of secondary prevention in patients after ACS
- Patients prescribed dual antiplatelet therapy (contextual cohort) for the indication of secondary prevention after ACS
- Patients have provided signed, informed consent

#### 9.2.4 Patient Exclusion Criteria

Patient exclusion criteria are:

- Patients prescribed with oral anticoagulants including rivaroxaban within 6 months prior to the index date for any indication
- Patients commenced rivaroxaban between date of market launch (28th October 2014) for the indication of secondary prevention after ACS and study start (18th September 2015)

#### 9.2.5 Evaluable cohort

Evaluable patients are those patients who have provided consent and for whom analysable clinical data has been provided in the data collection questionnaires. Evaluable patients for whom the 12 week survey questionnaire (from both specialist HCP and GP) is returned blank (contain no clinical information) or has not been returned will Version 7 Date: 30/08/2017

only be included for analysis of secondary and exploratory objectives, where appropriate.

Consented patients will not be considered evaluable if the specialist HCP reports that the patient did not take either combination therapies. If there is evidence to suggest duplication of patients, either through inadvertent duplication between different prescribers within the same clinical setting, or if a patient was switched from one combination therapy to the other, then the records identified will be considered for inclusion on a case by case basis by the advisory committee.

Patients will be automatically withdrawn if the patient or specialist HCP provides informed written or verbal notification that they no longer wish to participate at any stage of the study.

#### 9.3 Variables

#### 9.3.1 Eligible patient baseline information

For all eligible patients invited to participate, the following anonymised information will be collected on a baseline questionnaire from the specialist HCP using information contained within medical charts:

- Demographic characteristics (age, gender)
- Setting of first prescription- (e.g. inpatient hospital ward, outpatient clinic)
- Reasons for prescribing (clinical judgement, recommendation from NICE, expert committee guidelines, trust formulary committee guidelines)
- Which anticoagulant/antiplatelet regimen was prescribed and start date
- Clinical condition requiring anticoagulant/antiplatelet therapy (indication) and details of the clinical condition (e.g. STEMI, NSTEMI)
- Any prior anticoagulant/antiplatelet treatment
- Risk factors for bleeding at baseline (e.g. creatinine, white cell count, anaemia, presentation, antithrombotic medications)

#### 9.3.2 Patient 12 week end of observation questionnaire

For evaluable patients providing consent and for whom a completed baseline questionnaire has been received by the DSRU, at least 13 weeks after starting antiplatelet therapy, a second questionnaire will be systematically generated to collect clinical information from the specialist HCP relevant to start of observation and any clinical events of medical interest as recorded in the medical charts during the first 13 weeks (to ensure a full 12 week observation period post index date for each patient).

Data obtained from the 12-week end of observation questionnaire will include: Version 7 Date: 30/08/2017

- Additional information on anticoagulation treatment regimen:
  - Details of prior use of oral and parenteral anticoagulant and antiplatelet therapy (e.g. thienopyridines, aspirin, glycoprotein IIb/IIa inhibitors, heparins) in the past 12 months if known
  - Treatment regimen during the 12 weeks observation period
  - If study treatment regimen has changed: date and reason for change, details of transition plan to alternative; if required, details of reversal of anticoagulation therapy and management of bleeding complication
- Recent (< 4 weeks prior to index date) and concomitant medications (at index or during treatment):
  - not recommended for concomitant use (including azole antimycotics [e.g. ketoconazole] and HIV protease inhibitors)
  - to be used with caution (including fluconazole, strong CYP3A4 inducers, strong P-gp inhibitors, non-steroidal anti-inflammatory drugs (NSAIDs), acetylsalicylic acid, oral steroids, hormone and oral contraceptive therapy, platelet aggregation inhibitors or other antithrombotic agents)
- Medical history relevant for important potential, identified and special risks of interest (plus dates of first diagnosis/report)
- Specific information on renal function status and creatinine clearance at index date and any changes during 12 week observation period
- Specific information on hepatic disorders present at index date and any recent abnormal liver function tests
- Event reports including selected risks of interest (Table 3)
- Cause and date of death (if died) in the first 12 weeks after starting treatment;
- Behaviours prior to and/or starting treatment (e.g. smoking, alcohol/substance misuse)
- Demographic characteristics of specialist HCP; (age, sex, ethnicity, medical profession, year of first registration as HCP and awarding institution, specialism and year of first registration as specialist and awarding institution, year of start of employment at current institution)
- $\circ$  Institution type (teaching, general, private) and region of location
- Participation response/non-response rates (of eligible specialist HCPs within relevant existing research networks where available)

#### Table 3. Selected events of interest requiring further evaluation

Risk/Missing Information	Proposed data	Comment							
	capture								
IDENTIFIED, POTENTIAL AND SPECIAL RISKS AND OUTCOMES for targeted data collection									
on SCEM questionnaires									
Non CABG major bleeding episode	Targeted outcome	Selected risk factors collected on							
	questions on major	SCEM questionnaire. Further data							
	bleeds	on severity, management and risk							

		factors to be collected via follow-			
		up.			
Non CABG minor bleeding episodes	Targeted outcome	Selected risk factors collected on			
	question on minor	SCEM questionnaire. Not for			
	bleeds	follow-up			
Overdose, accidental trauma and	Targeted outcome	Events of overdose (dose > 50mg/day) and accidental trauma are those of clinical medical			
Reversal of anticoagulation	question				
therapy		importance which require acute			
		medical/surgical treatment (with or			
		without) hospitalisation Further			
		data may be collected via follow-			
		up			
Management of homeostasis	Targeted outcome	Data on management of			
	question	homeostasis in patients reported			
		with events of surgery (elective or			
		urgent ) during the observation			
		period will be collected via follow-			
Increased liver transaminases and	Targeted outcome	up Data on diagnosis of hepatic			
Gamma-Glutamyl Transferase	question	failure and where abnormal			
(GGT)	4	laboratory results indicate 3 X ULN			
		relevant parameters will be			
		collected via follow-up.			
Concomitant use of	Targeted outcome	Further data may be collected via			
contraindicated medications and	question on other	follow-up			
medications to be used with	medications to gather				
caution	duration and changes				
IMPORTANT MISSING INFORMATIO					
Use during pregnancy and lactation	General event report	Further data to be collected via follow-up			
		τοποιν-αμ			

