#### 8.2 Objectives:

Primary objective

- to quantify the cumulative incidence (risk and rate) of major bleeding according to the TIMI classification of non-CABG Related Bleeding (Table 1) occurring in the 12 week observation period, overall and stratified by the following bleeding sites:
  - o Intracranial,
  - o Gastrointestinal
  - o Urogenital

Secondary objectives

- 1. Advancing the understanding of the patient population prescribed rivaroxaban in combination with standard oral antiplatelet therapy for ACS in the secondary care hospital setting including drug utilisation characteristics
- 2. Describing changes of health profile of patients, assessment of adherence, number of indication related episodes (ACS related events), plus any alterations of the treatment programme in respect of antiplatelet and anticoagulant therapy during the 12 week study observation period
- 3. Quantifying the risk of other major (in any other site not specified in the primary objective) or minor bleeding outcomes (in any site) reported in the 12 week observation period overall (Tables 1 and 2) and, if number of reports are sufficient, in patient subgroups of special interest in first 12 weeks of treatment under conditions of the routine secondary care hospital setting in England and Wales.

Both the primary and secondary objectives relate to the rivaroxaban cohort and the contextual comparator (reference) cohort.

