#### 9.5 Study Size

The ability to detect an adverse event is dependent on the expected incidence rate of the adverse event in those exposed to the drug, the background rate in those not exposed to the drug, and the total number of patients.

Where studies, such as clinical trials, have already estimated the impact of the exposure on the outcome of interest, the objective should be to estimate the magnitude of the effect as precisely as possible (21). As such, in this study it is more appropriate to choose a sample size that will yield a confidence interval of a predefined width for those identified risks defined within the primary outcome which are of greatest clinical and medical importance i.e. major bleeding outcomes. Table 4 displays the samples sizes (95% confidence intervals) across a range of expected incidences and levels of precision. From rivaroxaban clinical trial data, the cumulative incidence risk of first occurrence of adjudicated major bleeding events (intracranial, GI and urogenital) in patients taking rivaroxaban for secondary prevention after ACS over the first 12 weeks of treatment was approximately 0.5% (0.1%, 0.3% and 0.1%). Thus in this population of patients with ACS treated with rivaroxaban, in order to estimate the expected (true) cumulative incidence of primary outcomes of major bleeding events of 0.5% within +/- 0.4%, we would ideally need a sample size of 1193 patients (Table 4). An equivalent number of patients within the contextual comparator cohort is desirable.

Incidence									
from RCT	Precision								
(%)	0.2%	0.3%	0.4%	0.5%	0.6%	1%	2%	3%	5%
0.10	958	426	240	153	107	38	10	4	2
0.20	1913	851	479	307	213	77	19	9	3
0.30	2864	1275	718	459	319	115	29	13	5
0.40	3812	1698	956	612	425	153	38	17	6
0.50	4755	2119	1193	764	531	191	48	21	8
0.70	6631	2958	1666	1067	741	267	67	30	11
0.80	7564	3376	1902	1218	846	305	76	34	12
1.00	9418	4208	2371	1519	1055	380	95	42	15
1.25	11716	5241	2955	1893	1315	474	119	53	19
1.50	13991	6267	3535	2265	1574	567	142	63	23
2.00	18475	8296	4684	3003	2087	752	188	84	30
3.00	27187	12268	6938	4452	3096	1117	279	124	45
4.00	35566	16126	9135	5866	4081	1473	369	164	59
5.00	43627	19871	11276	7246	5043	1821	456	203	73

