# Table 4.Sample sizes of evaluable patients required to estimate the
expected (true) cumulative incidence of a specified adverse event
with 95% confidence intervals of different precisions (0.2% to
5%).

#### 9.6 Data Management

#### 9.6.1 Data Processing

Specialist HCP/ GP/ patient identifiable information will be stored within a unique database. All original documents and individual correspondence from HCPs will be stored for 15 years at the DSRU, with considerable care taken to preserve patient confidentiality (see below).

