For each individual case, relevant person-time will be estimated according to duration of observation up to event date. For each individual non-case, relevant person-time will estimated by either exit date – index date; or censor date – index date; or stop date (+ 2 days ) – index date. For each cohort separately, a semi-parametric time-dependent Cox Proportional Hazards regression model will be used to estimate the crude cumulative incidence over the 12 week observation period.

Non-parametric Kaplan-Meier plots will be presented to describe time-to event as well as smoothed estimates of the empirical hazard function to describe how the crude baseline risk of the event changes over time.

Estimates of the hazard function will also be modelled to determine whether the baseline hazard (risk) of the event increases or decreases with time. A constant hazard over time may be consistent with a background (not caused by the drug) event rate, whereas a non-constant hazard over time may be an indicator of a drug-event relationship. The null hypothesis that the hazard rate of the selected event in patients will be constant during the 12 week period following the start of treatment will be tested

<sup>1 This excludes patients prescribed rivaroxaban 2.5mg for non-ACS related indications

<sup>2 Censor date = date of loss to follow-up

<sup>3 2 days allocated to person-time to account for half-life of drug

Version 7 Date: 30/08/2017

by fitting a parametric time to event model (e.g. Weibull). Such models have a shape parameter that indicates whether the hazard is significantly increasing or decreasing over time. At least five reports of an event are deemed necessary for modelling purposes.

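### CABG-related major bleeding is defined in Tables 1 and 2, which the secondary and exploratory objectives cite, but Table 3 targets only non-CABG bleeds, so it is not systematically collected

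*Protocol*

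**What the plan says.** Section 8.2 restricts the primary objective to TIMI major bleeding not related to CABG, overall and by three sites. Table 1 is headed for use in all three levels of objective. After the non-CABG definitions it adds: "A CABG related major bleeding event will be defined using TIMI criteria as any of the following bleeding events that were CABG related", with five criteria.

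Table 2 (BARC) is limited to the secondary and exploratory objectives, and its type 4 is CABG-related bleeding. Its footnote holds the only rule that ties a bleed to CABG by time. It begins "If a bleeding event occurs with a clear temporal relationship to CABG (ie, within a 48-h time frame" and goes on to classify such a bleed as no bleeding event if it falls short of type 4 severity.

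Secondary objective 3 covers "other major (in any other site not specified in the primary objective" and minor bleeding at any site, with a reference to Tables 1 and 2. Exploratory objective 2 (rivaroxaban cohort only) also refers to both tables for major bleeds. Neither mentions CABG.

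Table 3 (Section 9.3.2) sets out the targeted data collection. Its two bleeding rows are "Non CABG major bleeding episode" and the equivalent non-CABG minor row. The GP form (Section 9.3.3) takes its event reports from Table 3. An expert panel adjudicates reported primary events (Section 9.7.1).

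**The concern.** A category of major bleeding is defined twice, in tables that two objectives cite, but has no targeted row. A later analysis plan cannot repair this, because it can only analyse what the forms requested.

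The same labelling touches the primary outcome. A bleed in one of the three sites enters the primary numerator only if it is not CABG related, and Table 1 gives no rule for deciding that. If the form follows the Table 3 row label, a clinician could leave out a bleed after CABG as not being what was asked for, and the panel would then have nothing to adjudicate. The sensitivity analysis of all reported cases regardless of adjudication (Section 9.7.1) would not recover it either.

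CABG during observation is foreseeable. Observation starts with the acute management of the ACS (Section 9.1), the same section makes standard care depend partly on later surgery, and Table 3 expects elective or urgent surgery during observation.

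**Working it through.** **1. Definitions set against collection.**

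| Bleed | Defined in | Objective that can use it | Row in Table 3 |
|---|---|---|---|
| Non-CABG major, three named sites | Table 1 | Primary | Yes |
| Non-CABG major, other sites | Tables 1 and 2 | Secondary 3 | Yes |
| Non-CABG minor | Table 1 | Secondary 3 | Yes |
| CABG-related major | Table 1 (CABG block), Table 2 (type 4) | Secondary 3 and exploratory 2, neither of which excludes it | None |

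The primary objective is non-CABG by design, so the CABG definitions can supply an outcome only to the secondary and exploratory objectives.

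**2. Is there a TIMI rule for CABG-relatedness?** The 48-hour and 24-hour limits in Table 1's CABG block measure transfusion and chest tube output. They do not say when a bleed counts as CABG related. The 48-hour rule in Table 2 belongs to BARC, which is not used for the primary outcome. So no TIMI rule is stated.

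**3. The plan's own sample size.** Inputs from Section 9.5: "cumulative incidence of primary outcomes of major bleeding events of 0.5% within +/- 0.4" (per cent); Table 4 caption, "with 95% confidence intervals of different precisions"; and "we would ideally need a sample size of 1193 patients (Table 4".

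n = z² p(1 − p) / d² = 1.96² x 0.005 x 0.995 / 0.004² = 1194.5

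With a finite population correction, n / (1 + (n − 1)/N), and an assumed N of 1,000,000, this gives 1193.0. The stated figure is reproduced, and this point does not affect it.

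**4. Expected primary events.** 1193 x 0.005 = 5.97, or about 6 per cohort. Section 9.7.1 sets a floor for hazard modelling: "At least five reports of an event are deemed necessary for modelling purposes".

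**5. Sensitivity of the primary count.** Let f be the share of true primary events set aside as CABG related before adjudication. The documents give no value, so f is purely an assumption. Expected count = 5.97 x (1 − f):

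| f | Expected events | Apparent risk |
|---|---|---|
| 0% | 6.0 | 0.50% |
| 10% | 5.4 | 0.45% |
| 20% | 4.8 | 0.40% |
| 30% | 4.2 | 0.35% |
| 50% | 3.0 | 0.25% |

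The expected count passes below five at f = 1 − 5/5.97 = 16%.

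**6. Bleeds in patients who have CABG.** Assume that 3% to 10% of 1193 patients have CABG within 12 weeks (36 to 119 patients) and that 2% to 10% of those have a major bleed. Then 1193 x 0.03 x 0.02 = 0.7 and 1193 x 0.10 x 0.10 = 11.9, so roughly 1 to 12 per cohort. Both rates are assumptions. The count covers every major bleed in CABG patients, so it does not estimate lost primary events and should not be compared with the 6 in step 4.

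**The case against.** The questionnaires are not among the documents, and a row label is not form wording. The data-capture column of Table 3 speaks of questions on major and minor bleeds with no CABG restriction. A reader might infer that the clinician must judge CABG-relatedness before reporting, or that such bleeds never reach the panel. The documents support neither inference.

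Several backstops exist. The specialist form takes event reports that include, but are not limited to, Table 3 (Section 9.3.2). Free-text events are coded (Section 9.6.1.2). Table 3 prompts follow-up for patients with reported surgery, and all reported deaths are followed up (Section 9.3.4). The panel uses all available information and can reclassify (Section 9.7.1). The GP form covers only the time after discharge, so its limit to Table 3 does not affect bleeds during the surgical admission.

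It can also be said that secondary objective 3 separates other major bleeds by site and never names CABG-related bleeding, so Table 1's CABG block may be there only to mark off what the primary outcome excludes. The wording allows that reading, but it does not explain why BARC type 4 is also listed for the secondary and exploratory objectives.

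What stands of the objection is that these bleeds may be caught in part. What it does not supply is an item that asks for them, or a stated TIMI rule for separating them.

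**Conclusion.** The mismatch is real. CABG-related major bleeding is defined for objectives that cite Tables 1 and 2, and no targeted item collects it. Whatever the backstops yield will be incomplete to an unknown degree. The CABG split that governs the primary numerator has no TIMI rule, and the reporter may apply it before the panel does.

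The size is unknown because no CABG rate is given. Leaving CABG-related bleeds out of the primary outcome is by design and is not a fault. A reader might infer that the primary incidence is biased low. That would require non-CABG bleeds in the three sites to be wrongly withheld and missed by every backstop, and nothing in the documents shows how often that would happen. The effect on primary incidence is probably small, and the table of assumed shares shows only how sensitive a count of about 6 would be.

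A reader might also infer that the 48-hour limit makes a gastrointestinal bleed ten days after CABG a primary event. It does not, because that limit is a BARC rule and the primary outcome is TIMI.

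**What to change.** - In Table 3 and on both 12-week forms (specialist and GP), ask for any major bleeding, with the date of the bleed and the date of any CABG.
- State in Section 9.7.1 that the existing expert panel assigns CABG-relatedness for TIMI under a rule written in advance. Do not carry over the BARC 48-hour window, because its footnote also discards some bleeds close to CABG.
- Report CABG-related major bleeding (Table 1 CABG criteria, BARC type 4) as a separate line under secondary objective 3.

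The cost is two date fields, a revised form question, one table line and a few more bleeds for the panel. Recruitment began on 18 September 2015, so forms already returned will carry the existing item. The report should say which patients were asked the revised question.
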